## 17.0 Sharing of Results with Individuals

All information will be kept confidential except such as is necessary to disclose in order to provide appropriate medical care to a study participant, in which case the participant will be notified and their healthcare provider will be contacted via phone and/or fax. If a participant is found to have severe depression, they will be referred to appropriate health care providers. If a participant's blood tests positive for Hepatitis B, local laws may require that the result be reported to local health authorities.

## 18.0 Setting

Participants will be identified as eligible according to diagnosis, severity of symptoms and ability to give informed consent. Staff affiliated with this research study will conduct chart reviews as allowed by mental health centers to determine eligibility based on treatment history.

All research procedures will be performed at either the Northwestern University Department of Psychiatry and Behavioral Science offices located at [name] or the Stone Mental Health Center, located at [name]. For the Beacon Medical Group Behavioral Health South Bend site all research procedures will be done at either the Beacon Medical Group Behavioral Health South Bend [name] or the South Bend Medical Foundation [name].

# 20.0 Prior Approvals

Approval will be obtained from the Northwestern University IRB and the study sponsor, Janssen Research and Development, before commencing the research study.

#### 21.0 Recruitment Methods

Participants aged 18-60 with bipolar disorder of at least one year duration, as established by SCID-I, will be recruited for this study. Participants will be identified as eligible according to diagnosis, severity of symptoms and ability to give informed consent. The clinical treatment providers of potentially eligible participants will be notified of the inclusion and exclusion criteria for the study, by way of written communication or regularly scheduled presentations to the providers (e.g. lunch presentations, weekly therapist meetings, etc.), and will be asked to discuss the study with potential candidates. The research staff will meet with the participants only after notification of the current provider of psychiatric

services and after the participants have expressed interest in taking part in research.

We will utilize referrals from primary care or psychiatry providers, or from participant interest and consent. We will also be recruiting individuals through the NU-SRG Recruitment Pipeline (STU00059328).

As part of the NU-SRG Recruitment Pipeline, research staff will first read individuals a verbal consent, where they can indicate if they are interested in completing a screening form and if we can hold onto their information and contact them for future research opportunities. We have prepared handouts with a flow chart to help guide candidates and clinicians to determine if candidates are preliminarily eligible for the study. We then complete a 5-10 minute screening form to determine eligibility for the study. The PI, the sub-investigator, and fully trained research staff will determine initial prescreen eligibility. The PI will personally review and approve all enrollees prior to randomization.

#### 22.0 Local Number of Individuals

After screening for eligibility and providing written informed consent, 60 stable outpatients, who may have mild-moderate depressive symptoms, will be randomized to receive adjunctive treatment with either JNJ-18038683 or placebo.

We propose to study a total of 60 randomized participants, 30 receiving JNJ-18038683 and 30 randomized to placebo.

## 23.0 Confidentiality

All data that will be stored on sites and will be maintained in locked cabinets (double lock rule applies). Blood specimens will be processed locally at Northwestern Memorial Hospital and South Bend Medical Foundation. Only NU-IRB approved members of the study team will have access to the study data. De-identified data will be kept separately from the identified data. De-identifiable data will be entered into a RedCap data base that serves as an Electronic Data Capture (EDC) system,

## 24.0 Provisions to Protect the Privacy Interests of Individuals

Participants will be reminded whenever appropriate that they are at liberty to opt out of answering any questions or undergoing any procedures with which they are not comfortable, up to and including their right to rescind their participation in the study without any penalty unto them.

Participants must sign an authorization for release of information before any sources of information can be contacted about the participant.

# 25.0 Compensation for Research-Related Injury

- 25.1 If the research involves more than Minimal Risk to individuals, describe the available compensation in the event of research-related injury.
- 25.2 Provide a copy of contract language, if any, relevant to compensation for research-related injury.

#### 26.0 Economic Burden to Individuals

Participants may incur costs related to transportation by participating in this study, and they will be reimbursed for part or all of such incurred expenses.

Individuals will be compensated at the rate of \$40/visit for their time and effort. The total amount for visit compensation will be prorated based on subject's participation. Up to \$20 per visit will also be provided to cover individuals' transportation and parking expenses. For any visit lasting over 4 hours \$10 will be provided to cover subject's lunch costs.

#### 27.0 Consent Process

The informed consent form will typically first be discussed with a potential participant over telephone, and after the participant has considered their ability to participate in the study, will again formally be reviewed with the participant during an in-person screening visit at the Northwestern University Department of Psychiatry and Behavioral Science offices or at the Beacon Medical Group Behavioral Health South Bend. Any time that there is a change in the protocol or the informed consent form, the revised consent form will again be reviewed with and signed by the participant. Individuals obtaining consent will follow 'SOP: Informed Consent Process for Research (HRP-090).'

No non-English speaking participants, minors, cognitively impaired adults, or adults unable to provide consent will be considered for participation in this study, nor will any waivers or alterations of the consent process be applied for.

## 28.0 Process to Document Consent in Writing

Individuals documenting the consent in writing will follow 'SOP: Written Documentation of Consent (HRP-091).'

## 29.0 Drugs or Devices

JNJ-18038683 will be provided by Janssen Research and Development, the makers of JNJ-18038683, and will provide a detailed Certificate of Analysis attesting to the contents of the product.

The investigational product has been assigned the number JNJ-18038683-ADC. The suffix ADC denotes the citrate salt form and JNJ-18038683-ADC is referred

to as JNJ-18038683 unless stated otherwise. Alternatively, the number RWJ-800054 may also be used to denote the citrate salt form.

The full International Union of Pure and Applied Chemistry (IUPAC) chemical name is 3-(4-chlorophenyl)-1,4,5,6,7,8-hexahydro-1-(phenylmethyl)pyrazolo[3,4-d]azepine 2-hydroxy-1,2,3-propanetricarboxylate (1:1). JNJ-18038683 has been assigned the Chemical Abstract Service (CAS) registry number 851376-05-1.

An oral solid dosage formulation has been manufactured as tablets containing 10 mg of JNJ-18038683, lactose monohydrate, croscarmellose sodium, povidone, silicified microcrystalline cellulose, and magnesium stearate. The placebo formulation will be supplied as matching tablets. Detailed instructions for storage conditions and oral dose administration will accompany the clinical drug supplies to the clinical study sites.

The target dosage will be 20 mg/day, or 2 tablets of 10 mg once per day. This will preserve the blind, as the placebo comparator will be also given as 2 tablets once per day. Individuals will receive 10 mg/day for the first week, and 20 mg from weeks 2-7 with a provision for a single, downward, dose adjustment.

Study clinicians will be responsible for dispensing JNJ-18038683 at our research office. An unblinded study drug manager will receive and label and distribute the product for dispensing during the study.

At the baseline and end of study visits, measures of safety and effectiveness will be administered and individuals will be evaluated for response and side effects to the treatment. To assess adherence to dosing of the agent, the study medication will be returned and counted.

Study drugs sent by the sponsor to the study site will be stored in a locked cabinet and be handled only by the study coordinator, who will also maintain drug accountability logs and drug destruction/return logs that will be verified by the site monitor to ensure that study drugs have only been used on individuals and only by authorized investigators.

Study Drug/Study Device: JNJ-18038683

IND/IDE Number: 126601

IND/IDE Holder Name: [name]

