#### 9.0 Procedures Involved

Study visits will include screening and 6 visits (baseline, Weeks 1, 2, 4, 6, and 8). Please see Appendix 1 – Schedule of Assessments

At screening, the Structured Clinical Interview for Diagnosis for DSM Disorders (SCID) will be completed for confirmation of psychiatric diagnosis. A medical/psychiatric history will also be collected and a physical exam will be performed. Vital signs including weight, height, waist and hip measurement will be obtained at screening to record body mass index. The Hopkins Verbal Learning Test (HVLT) and Trail Making Test A (TMT-A), will be administered to screen for severity of cognitive impairment. Only individuals who score between the 25th and 75th percentile as compared to normative data on these tasks will be enrolled.

If the subject is determined eligible during the screening procedure, which can last for up to two weeks, a baseline visit will be scheduled. Baseline assessments of cognitive function, psychopathology and global function will be administered along with movement ratings at the baseline visit. Functional outcome will be assessed with Specific Level of Function Scale (SLOF) [33]. Adverse events will be collected and recorded from the time the subject signs the informed consent to the final safety follow-up visit, and motor side effects will be monitored by the Abnormal Involuntary Movement Scale at the following visits: baseline, Weeks 4 and 8.

Individuals will be randomized to receive JNJ-18038683 or placebo after the completion of the baseline assessments. Individuals will be stratified for randomization as either being treated with an AD or not being treated with an AD. As in the previous study of JNJ-18038683 for depression, individuals randomized to JNJ-18038683 will receive 10 mg for one week, then titrate to 20 mg, with the provision for a single, downward dose adjustment for intolerance, based upon investigator judgment. No antipsychotic drugs which are 5-HT7 antagonists will be permitted to avoid effects upon 5-HT7 receptors from enhanced 5-HT concentrations and possible down regulation of 5-HT7 receptors. As JNJ-18038683 is a competitive inhibitor of CYP2D6, there will be a 2 week washout period requested after the trial prior to initiation of any CYP2D6 substrates (see Appendix 2).

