Individuals will be asked to return to the clinic at study weeks 1, 2, 4, and 6 after baseline to monitor for side effects and compliance. At the Week 4 visit, efficacy assessments will be completed (MADRS, YMRS and CGI-BP). Between clinic visits, research staff will complete phone calls with individuals at study Weeks 3, 5, and 7. Individuals will return for a final study visit 8 weeks after initiation of the randomized study medication. A Safety Follow-up phone call will take place 4 weeks after the final visit and safety assessments will be completed (C-SSRS, Adverse Events, Concomitant Medications). The assessments completed at baseline will be repeated at this Week 8 visit (See Appendix 1 – Schedule of Assessments). Reasons for early termination will be recorded. Every effort will be made to obtain appropriate rating scale data at the final visit of early terminators.

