#### 9.3 Adverse Events

In a 7 week, randomized, placebo controlled trial comparing JNJ-18038683 with placebo and escitalopram (an active comparator), a total of 6 serious adverse events were reported during the study (placebo group: spontaneous abortion and suicidal ideation; escitalopram group: spontaneous abortion, suicidal ideation, suicide attempt, and chest discomfort). A total of 10 individuals (3 in the placebo group, 4 in the JNJ-18038683 group, and 3 in the escitalopram group) were withdrawn from the study prematurely due to adverse events. The 4 events leading to drop out of individuals on JNJ-18038683 were one instance each of the following: bundle branch block, panic attack, upper respiratory infection, and insomnia.

Only 3 individuals receiving the 20-mg dose of JNJ 18038683 required dose reductions at any point during the study.

Adverse events that were reported in more than 5% of individuals in any treatment group included headache, nausea, nasopharyngitis, insomnia, somnolence, dyspepsia, dizziness, dry mouth, constipation, diarrhea, vomiting, back pain, upper respiratory tract infection, palpitations, and fatigue. The treatment-emergent adverse events that were reported more frequently in the JNJ 18038683 group compared with the placebo or escitalopram groups included dyspepsia, constipation, upper respiratory tract infection, and palpitations.

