#### 9.5.2 Columbia Suicide Severity Rating Scale

The C-SSRS was developed by a team of researchers at Columbia University to address the need for standardized classification of suicide reports to assess suicide risk. This scale consists of a baseline evaluation that assesses the lifetime experience of the subject with suicide events and suicidal ideation and a post-baseline evaluation that focuses on suicidality since the last study visit. A baseline C-SSRS will be completed at the screening visit. The C-SSRS Since Last Visit form will be completed at all subsequent visits and telephone calls (Day 21, Day 35, and Day 49).

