## 11.0 Data and Specimen Management

#### 11.1 Data Analysis Plan

The primary analysis will be a mixed model repeated measures ANCOVA adjusting for baseline differences in dependent measures, sex and race. Missing data will be imputed by MMRM. We would also examine some variables categorically.

Assumptions for the power analysis included random assignment into one group receiving placebo and one JNJ-18038683. The cognitive battery, as the primary instrument, will be collected at baseline and at end point (8 weeks). Using repeated measure ANCOVA, the time average difference in the response variable will be compared between groups to detect treatment difference. Based on Javitt et al, 2012, we assume the mean baseline verbal learning score will be 36.2, SD 9.4 for both groups. We are assuming the placebo group will show no improvement while the treatment group will improve a mean of 5 points, a medium effect. We assume the correlation coefficient of repeated observation to be 0.5 and the covariance structure to be compound symmetry. The power calculation was conducted with alpha level of 0.05 using one-sided and two-sided tests. Full results are available upon request. With a one sided test, 33 individuals per group are required assuming 5 points improvement of the treatment group compared to the placebo for the desired power of 80% with alpha level of 0.05. We plan to recruit 36 per group to account for drop outs. In the two sided test the sample size per group is 42.

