Data Analysis Plan for Northwestern- Janssen R&D Collaboration Study

Protocol Title: Testing the ability of JNJ-18038683, a selective serotonin (5-HT)7 antagonist, to

improve cognition and reduce residual depressive symptoms in stable bipolar patients

Protocol Identifier Number: 18038683BCD2001

Northwestern University IRB Number: STU00200919-MOD0042

Version: 1.13

Date: 08.04.2021

Goals:

The goals of this study are to evaluate the efficacy of JNJ-18038683 in an 8-week trial to ameliorate the cognitive deficit and reduce residual depressive symptoms in 60 stable bipolar outpatients receiving treatment for depression. JNJ-18038683 will be studied and compared with placebo as adjunctive treatment to standard pharmacologic treatment for bipolar disorder. Sixty patients will be enrolled and randomized with a 1:1 ratio to one dose of JNJ-18038683 or placebo providing 30 subjects for each treatment arm. The initial intention was to follow stratified randomization based on the presence/absence of atypical APDs with 5-HT7 antagonism so that there is a balance in the assignment of active treatment and placebo in individuals who are and are not, receiving atypical APDs with 5-HT7 antagonism. However, due to recruitment difficulties, the stratified randomization method was not able to be followed as anticipated and was amended.

Assessments and Events:

Demographics, medical history, physical examination, serum pregnancy test, urine drug test, SCID-I diagnosis, and screening neurocognitive assessments will be done only during the screening visit. Urine pregnancy testing is performed at the baseline visit.

Table 1: Assessments completed during the screening visit only

Event /Assessment	Screen
Medical History & Demographics	X
Physical Examination	X
Serum Pregnancy Test	X
Urine Drug Screen	X
Inclusion/Exclusion Criteria	X
SCID-I	X
Screening neurocognitive assessments	X

Neurocognitive battery will be the primary measure of interest and evaluated at baseline and 8 weeks. The clinical global severity scores (CGI-BP), Young Mania Rating (YMRS), Scale for Tardive Dyskinesia (AIMS), Montgomery Asberg Depression Rating Scale (MADRS), Electrocardiogram and Clinical Safety Laboratory Tests will be collected at screening or baseline, and at 4 and 8 weeks. A measure of functional ability (SLOF) also will be assessed at baseline and 8 weeks. The schedule of these assessments is listed in table 2.

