The primary outcome measure for this study is verbal fluency performance as assessed with the Rey Auditory Verbal Learning Test, Rey Verbal Learning Test – Recognition Form, Verbal Fluency Test "Letterforms", and Animal Naming Test. The 8-week evaluation of verbal fluency after randomization is the primary outcome measure. Since the main interest is to measure the treatment effect for verbal fluency improvement from baseline and there is only one follow-up time point for the primary outcome variable, an ANCOVA model will be best suited for this study to compare the treatment effect using baseline value as a covariate. Alternatively, an ANOVA model will be used to compare the percent improvement and changes in the verbal fluency scores across treatment groups. Also, we plan to compare the treatment effect on verbal fluency performance over time using a mixed model. The missing evaluations will be imputed with the last value carried forward method, while model fit statistics will be used to estimate the appropriate covariance structure for this model.

There is both preclinical and clinical evidence that age has an important influence on 5-HT7 receptor function, which is the target of JNJ-18038683. Capacity to respond to JNJ-18038683 may decline with age. Thus, we predict the age of the subject will be related to the extent of improvement in verbal fluency and other measurements in the cognition battery. The relationship of age and percent improvement and the direct change of verbal fluency from baseline to 8 weeks in each treatment arm will be assessed using correlation analysis. The age variable will be used as a continuous variable in the analysis. If the distribution of the age variable is skewed, then age groups will be formed appropriately. In the above described ANCOVA and repeated measures models, age will be use as a covariate to assess the treatment effect. Graphical methods will be used to check for any inflection points of improvement of verbal fluency score in the treatment group compared to placebo. In the treatment group, better improvement is expected in younger patients compared to older patients. This relationship is not expected in placebo-treated patients. Additionally, with the above-mentioned models, the effect of covariates, MADRS total score, YMRS and Clinical Global Severity score on cognition will be examined because baseline mania or depression severity may influence performance on cognitive testing.

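### Section 29.0's stated dosing schedule runs only to Day 49 and gives no dose for week 8, while the sole post-baseline cognitive battery is on Day 56; most likely a drafting slip, but it should be corrected

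*Protocol*

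**What the plan says.** **Dose.** Protocol Section 29.0: "Individuals will receive 10 mg/day for the first week, and 20 mg from weeks 2-7", with one downward adjustment allowed. Section 9.0 also describes the titration: "As in the previous study of JNJ-18038683 for depression, individuals randomized to JNJ-18038683 will receive 10 mg for one week", after which patients go up to 20 mg. Section 9.0 gives no end to the 20 mg period.

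**Calendar.** Section 9.0 says that "research staff will complete phone calls with individuals at study Weeks 3, 5, and 7", and Section 9.5.2 dates those calls Day 21, Day 35 and Day 49. The final visit is 8 weeks after study medication starts, and both schedules of assessments (Section 7.0 and Appendix 1) put it on Day 56.

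**Primary measurement.** The SAP, under Assessments and Events: "Neurocognitive battery will be the primary measure of interest and evaluated at baseline and 8 weeks". Under its primary efficacy analysis: "The 8-week evaluation of verbal fluency after randomization is the primary outcome measure". The SAP adds that there is a single follow-up time point for this variable. Protocol Section 11.1 and both schedules agree that Day 56 is the only post-baseline battery.

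**Stated lengths.** Section 1.0 describes an 8-week trial. Section 9.4.9.1 refers to a 9-week treatment phase, and Section 9.4.6 places the end-of-study visit at Week 9.

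**The concern.** Section 29.0 is the only dosing statement with an end week, and that week falls short of the only visit at which the primary outcome is measured after baseline. A site that followed it literally would test patients about a week after their last tablet. A site that took the trial to mean eight weeks of treatment would test them on drug.

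These are different quantities. The first is what remains of the effect a week after stopping; the second is the effect during treatment. With a single post-baseline battery, no earlier on-drug cognitive measurement could stand in if the Day 56 one were taken off drug.

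**Working it through.** **Inputs.** 10 mg/day in week 1 and 20 mg/day in weeks 2-7 (Section 29.0); week 7 equals Day 49 (Sections 9.0 and 9.5.2); final visit and battery on Day 56 (both schedules, Section 11.1, SAP). Assumptions: first dose on Day 1, full adherence, no dose reduction.

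**Step 1: what weeks 2-7 means in days.** Week w covers Days 7(w - 1) + 1 to 7w.
- Week 1: Days 1-7.
- Weeks 2-7: Days 8-49.
- Week 8: Days 50-56, with no stated dose.

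This agrees with the dates of the week 3, 5 and 7 calls: 7 × 3 = 21, 7 × 5 = 35, 7 × 7 = 49.

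**Step 2: can another numbering rescue the text?** Counting from week 0 puts weeks 2-7 at Days 15-56, which reaches the final visit. But Days 8-14 then have no dose, against Section 9.0, which moves patients to 20 mg after one week. It also conflicts with the call dates. No numbering fits cleanly.

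**Step 3: the gap and the exposure.**

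| | Last dose Day 49 | Last dose Day 55 | Last dose Day 56 |
|---|---|---|---|
| Days at 20 mg | 42 | 48 | 49 |
| Total dose | 70 + 840 = 910 mg | 70 + 960 = 1,030 mg | 70 + 980 = 1,050 mg |
| Days from last dose to battery | 7 | 1 | 0 |

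The literal schedule gives 140 mg less than dosing through Day 56: 140/1,050 = 13.3%.

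**Step 4: power.** Section 11.1 assumes a 5-point difference, SD 9.4 and correlation 0.5. The SD of the two-point average is 9.4 × √((1 + 0.5)/2) = 8.141. With 33 per arm and one-sided alpha of 0.05, power is 0.8024, matching the stated 0.80235. Dosing length does not enter this calculation. To adjust the 5 points for a week off drug would need a half-life or data on how quickly a cognitive effect fades, and the documents give neither. The two-week washout before CYP2D6 substrates is a precaution against interactions and does not supply that information.

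**Step 5: which length was meant?** Evidence for dosing to Day 56:
- Section 9.0's 20 mg has no end, in a trial described as 8 weeks long.
- The only washout is after the trial, and no drug-free week is described.
- The Day 49 contact is a telephone call, with no procedure for stopping or collecting drug.
- Section 29.0 has medication returned and counted, in the paragraph on the baseline and end-of-study visits.

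Evidence for a planned stop at Day 49: the weeks 2-7 wording alone.

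**The case against.** The strongest reply is that Section 29.0 contains no instruction to stop. It only leaves week 8 without a dose, and Section 9.0 read with the 8-week trial length naturally gives 20 mg until the final visit. Section 29.0 also says that detailed dosing instructions accompany the drug supplies. Those are not in these documents and may settle the stop day. On this view an off-drug primary measurement is unlikely.

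Most of this stands. It makes a slip the likely explanation, but it does not make the sentence right: an operative dosing section should not stop short of the primary visit.

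Four stronger readings are tempting and are not supported.
- *The primary outcome was measured off drug, or the two sites dosed differently.* No passage shows either; they are only possible under the wording.
- *The trial is biased or the type I error is raised.* The same schedule applies to both randomised, blinded arms, so neither follows.
- *Adherence and safety reporting are compromised.* The stop day does change the expected tablet count and moves the end of the 30-day post-dose window from Day 86 to Day 79. But no adherence threshold, analysis set or adherence analysis is planned. Adverse events are collected to the final safety follow-up, and the last contact is Day 84 either way.
- *The seven weeks were carried over from the earlier study.* Section 9.3 describes it thus: "In a 7 week, randomized, placebo controlled trial comparing JNJ-18038683 with placebo and escitalopram". That is a possible source, but the documents do not give that study's dosing weeks.

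**Conclusion.** Section 29.0 is wrong as written, or at best incomplete: its schedule ends on Day 49 and the only post-baseline primary measurement is on Day 56. Confidence is high for this inconsistency. It is not high for the idea that any patient was assessed off drug, since the surrounding text favours dosing to the final visit.

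Taken literally, the size is about 7 days off drug at the primary assessment, 7 fewer days at 20 mg and 13.3% less total dose. These figures assume a first dose on Day 1, full adherence and no dose reduction. Any loss of power cannot be quantified from the documents. The stated sample-size figures are unaffected as calculations. The correction is worth making because it concerns the one time point on which the efficacy conclusion rests, and it costs almost nothing.

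**What to change.** Change Section 29.0 to: *20 mg from weeks 2-8, with the last dose on the day of, or the day before, the Day 56 visit*. Align Week 9 in Section 9.4.6 and the 9-week phase in Section 9.4.9.1 to 8 weeks. The cost is three wording corrections.

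If seven weeks of dosing was intended, state that explicitly, including that the primary battery is taken about a week after the last dose. Moving from a genuine seven-week plan to eight weeks would add 7 × 20 = 140 mg per patient and would need an amendment, not a wording correction.

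The SAP describes patients as having already received drug. For them, change nothing. Optionally, report days from last dose to the Day 56 battery by arm, if the date of last dose was recorded. Section 9.4.10 requires the time of the last dose before each ECG but does not mention its date, so check that the date exists before committing to this summary.
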